4.2.3 Exploratory Endpoints

Although not a study aim, we will also report quality of life as an additional outcome. Quality of life will be measured using the HQLQ139 at baseline and 3, 6, and 9 months. Scores at 3, 6, and 9 months will be regressed on baseline scores to examine the effect of the intervention as compared with Usual Care. Effect sizes and 95% CIs will be reported for the effect of each intervention.

5 Study Enrollment and Withdrawal

5.1 Inclusion Criteria

In order to be eligible to participate in this study, an individual must meet all of the following criteria:

Persons will be eligible for HCV and HIV screening if they:

- (1) are 18 years or older,
- (2) injected heroin, cocaine, or other drugs in the past 30 days.

5.2 Exclusion Criteria

An individual who meets any of the following criteria will be excluded from participation in this study:

- (1) Persons already in care for hepatitis C, defined as having had at least 2 visits with a hepatitis treatment provider within the past 6 months, will be excluded.

5.3 Vulnerable Subjects

N/A

5.4 Strategies for Recruitment and Retention

The Lower East Side Harm Reduction Center is a community based syringe exchange programs in New York City. Through funding from the New York City Department of Health 'Check Hep C' program these facilities have been screening syringe exchange participants for hepatitis C. Subjects who have active hepatitis C infection through screening done by the partnering facilities will be referred to the study team for potential enrollment. Study staff will work with syringe program staff to recruit participants. Syringe program staff will refer participants from their program in person to onsite study staff. Recruitment will occur through word of mouth with planned information sessions scheduled at the syringe program's weekly hepatitis C support groups. We will also seek referrals from other organizations serving people who use drugs (methadone maintenance treatment programs, homeless services, harm reduction organizations). In partnership with those organizations, we will engage in active and passive recruitment strategies. Staff at the collaborating organization will engage in active recruitment by identifying potential participants and providing a direct referral to study staff (either by phone or using a referral form). A passive recruitment strategy will be the display of informational flyers at the collaborating sites (see attached flyer). The study flyer will include a brief description of the study, some inclusion criteria and contact information. Additional passive recruitment strategies will include posting and distributing study

flyers in areas where people who use drugs are known to congregate (e.g., parks, near street drug markets).

5.5 Duration of Study Participation

52 to 144 weeks

5.6 Total Number of Participants and Sites

500 participants approached, 300 participants randomized. No participants will be enrolled at NYUMC.

5.7 Participant Withdrawal or Termination

5.7.1 Reasons for Withdrawal or Termination

Participants are free to withdraw from participation in the study at any time upon request. An investigator may terminate participation in the study if:

- Any clinical adverse event (AE), laboratory abnormality, or other medical condition or situation occurs such that continued participation in the study would not be in the best interest of the participant
- The participant meets an exclusion criterion (either newly developed or not previously recognized) that precludes further study participation

5.7.2 Handling of Participant Withdrawals or Termination

We will make every effort must be made to undertake protocol-specified safety follow-up procedures to capture AEs, serious adverse events (SAEs), and unanticipated problems (UPs).

There will be no replacement of participants who withdraw or discontinue early. Data will be analyzed as intention-to-treat.

5.8 Premature Termination or Suspension of Study

This study may be temporarily suspended or prematurely terminated if there is sufficient reasonable cause. Written notification, documenting the reason for study suspension or termination, will be provided by the suspending or terminating party to <investigator, funding agency, the IND/IDE sponsor and regulatory authorities>. If the study is prematurely terminated or suspended, the PI will promptly inform the IRB and will provide the reason(s) for the termination or suspension.

Circumstances that may warrant termination or suspension include, but are not limited to:

- Determination of unexpected, significant, or unacceptable risk to participants
- Demonstration of efficacy that would warrant stopping
- Insufficient compliance to protocol requirements
- Data that are not sufficiently complete and/or evaluable
- Determination of futility

Study may resume once concerns about safety, protocol compliance, data quality are addressed and satisfy the sponsor, IRB and/or FDA.

6 Study Agent (Study drug, device, biologic, vaccine etc.) and/or Procedural Intervention

N/A

7 Study Procedures and Schedule

7.1 Study Procedures/Evaluations

Initial Research Visit (all participants):

1. After signing the consent form, participants will be asked to provide contact information, including your personal telephone number. Also, we will ask participants whether there are friends or family members that we can contact if we have lost contact with you for any reason. No personal health information will be shared with these family or friends. These persons will simply be asked to convey the message that the study team is interested in seeing you. Every month participants will be asked to briefly check in with the study staff, and participants be asked if there are any changes in your contact information.
2. A member of the study team will administer a detailed questionnaire at the time of enrollment into the study. This questionnaire will ask questions about participants' demographics (e.g., age, gender, race), alcohol and drug use history and practices, sexual behavior, and experience with health care.
3. Human Immunodeficiency Virus (HIV) Testing. Participants will have a 10-to 15-minute HIV prevention counseling session with a trained staff member. The session will cover the meaning of results from the HIV test. Participants will also learn about how to reduce your chances of being infected with HIV and other infectious diseases. Participants will get counseling about what the test result means. Participants can get the result of your HIV test within about 20 minutes. Participants will get also get post-test counseling from a trained staff member and referrals to services you may need. If participants already know they have infection with the HIV virus, they may provide results of their HIV test from their medical records instead of doing this test.

At the initial research visit, participants will be randomly assigned to one of these two groups:

Group A: Accessible Care

OR

Group B: Usual Care

If you take part in this study and are assigned to Group A, you will have the following tests and procedures:

Group A-Accessible Care (Hepatitis C Care at Lower East Side Harm Reduction Center) The study will follow participants while receiving, or being offered, treatment for their hepatitis C infection at the Lower East Side Harm Reduction Center. The hepatitis C treatment, and the medications participants may receive for it, are not being tested as part of the study. However, their response to treatment, and the laboratory tests taken as routine usual care during treatment will be used for study purposes.

Research only visits (every 3 mos): Information that will be collected for the study will consist of (1) detailed questionnaires, and (2) one or more extra blood tests. The details of the study are as follows:

1. Questionnaires will be administered every three months for up to 12 months, independent of whether participants receive treatment for your hepatitis C, with questions about their substance use history and practices, sexual practices, and experience with health care. These interviews can be conducted at the research site, in-person at a different location, or over the telephone.
2. Human Immunodeficiency Virus (HIV) Testing as described above will be offered at a research visit every 6 months to those participants who previously tested negative for HIV.

3. If participants' Hepatitis C is cured they will continue to be followed for up to 144 weeks after treatment completion for the duration of the study.

Hepatitis Care and Treatment:

4. Participants will be scheduled to see a hepatitis C medical doctor at your harm reduction facility (Lower East Side Harm Reduction). If a participant decides to attend the hepatitis C medical evaluation, a study doctors will evaluate them to find out whether you would benefit from treatment for hepatitis C. The doctor will ask participants questions, examine them, give them information, and answer their questions about hepatitis C, about treatment for hepatitis C, and about the risks and benefits of being treated. The purpose of the medical evaluation is to decide whether participants need treatment for your hepatitis C and what the best treatment would be. Participants will receive a standard medical evaluation to assess your Hepatitis C treatment needs.
5. At the medical evaluation, about 20mL (4teaspoons) of blood will also be drawn by one of the other research staff members, and sent to New York Presbyterian Hospital. The blood will be tested to assess participants' health and liver. A small percentage of the blood drawn will be stored at the Weill Cornell Medical College Clinical and Translational Science Center for future testing of characteristics of your hepatitis C virus.
6. We will schedule participants to come back in 2 weeks to find out the results of your blood tests. Participants and their hepatitis C doctor will work together to make an informed decision about whether participants will take medication used to treat hepatitis C. The doctor will explain the risks and benefits of taking any medicines before you take them. The medications the doctor will prescribe are the current best standard of HCV treatment available. If the doctor recommends that the participant take these medications, participants will be free to decide whether or not to take them.
7. If participants take the medication for hepatitis C, they will get appointments to come back to pick up their medication. Hepatitis C medications prescriptions will be sent to specialty pharmacies, and when obtained, delivery of medication will be to the harm reduction facility or patients residence if novel coronavirus is an issue.
8. If participants begin treatment for hepatitis C, standard blood tests for monitoring the treatment will be performed by a members of the research staff (or commercial lab testing centres if novel coronavirus is an issue), at weeks 2, 4 and 12 of treatment, and 4 and 12 weeks after the end of treatment. In addition, an extra two teaspoons of blood may be drawn at each of these visits for research purposes and sent for storage at Cornell's Clinical and Translational Science Center. These samples may be tested to look for signs of multiple concurrent hepatitis C infections, and help to decipher treatment failure from re-infection in participants who do not achieve cure of their hepatitis C.
9. If participants start the medications used to treat hepatitis C and want to stop them before their treatment is finished, they are free to do so and will not be penalized in any way, although this could limit the success of hepatitis C treatment. Participants will be encouraged to continue with the study questionnaires every three months.
10. Within 6 months of enrolling in the study, participants will have a one-on-one meeting with a hepatitis C study coordinator to review harm reduction practices. This discussion will include discussions on prevention of hepatitis C transmission and re-infection, ways to engage in safe injection practices and avoid cross-contamination of injection equipment while injecting with others.
11. Data from participants' clinical medical records will be entered into our research database during the course of your treatment by a members of the research staff. These data include, but are not limited to, hepatitis C genotype, hepatitis C viral load, fibrosure results(looking for signs of cirrhosis), HIV antibody, sustained virologic response (defined as no detectable hepatitis C virus 12 weeks after completing therapy), and any side effects or adverse effects you experience during therapy

If participants agree to take part in this study and are assigned to Group B, participants will have the following tests and procedures:

Group B –Usual Care Group (Hepatitis Care at usual locations in the community): If assigned to this group, participants will participate in research visits but not receive hepatitis care or treatment at the Lower East Side Harm Reduction Center as part of the study. Participants can obtain care and treatment for hepatitis C at the usual locations in the community.

Research Visits (every 3 mos): Information that will be collected for the study will consist of (1) detailed questionnaires, and (2) one or more extra blood tests. The details of the study are as follows:

1. Questionnaires will be administered every three months for up to 12 months, independent of whether participants receive treatment for your hepatitis C, with questions about their demographics (e.g., age, gender, race), their alcohol and drug use history and practices, sexual practices and experience with health care.
2. One teaspoon of your blood will be drawn and sent to New York Presbyterian Hospital –Weill Cornell Translation Science Center where it will be processed and stored for potential future testing of characteristics of your Hepatitis C virus.
3. Human Immunodeficiency Virus (HIV) testing as described above will be offered at a research visit every 6 months to those participants who previously tested negative for HIV.

Hepatitis Care and Treatment:

4. Participants will be referred to a hepatitis C case manager (funded through the New York City Department of Health Check Hep C Program), on site at their harm reduction facility (Lower East Side Harm Reduction Center), who will assist participants with referral for hepatitis C care within the community.
5. If participants start treatment for hepatitis C during their time in the study, we will ask participants to give us permission to talk with their hepatitis C doctor so we can have access to their medical records and monitor how they are responding to treatment.
6. If participants achieve a sustained virologic response after completing hepatitis C treatment, which means that the treatment was successful, participants will be given an appointment to come back every three months to complete a study interview and be tested for hepatitis C, for up to 144 weeks after treatment completion, to find out whether they are still negative, or to see whether they get re-infected.

QUALITATIVE INTERVIEWS During the study, we may ask participants to take part in an interview about their experiences related to hepatitis C treatment. This will last about 60-90-minutes. If participants choose to participate, the interview will be digitally audio-recorded. If participants are selected for this interview we will ask participants about: health care and hepatitis C-related healthcare experiences, alcohol and drug use, injection risk behaviors and sexual practices. We will ask participants how these changed, if they did, during their taking part in the study.

7.2 Concomitant Medications, Treatments, and Procedures

N/A

7.3 Justification for Sensitive Procedures

N/A

7.4 Prohibited Medications, Treatments, and Procedures

N/A

7.5 Prophylactic Medications, Treatments, and Procedures

N/A

7.6 Rescue Medications, Treatments, and Procedures

N/A

7.7 Participant Access to Study Agent at Study Closure

N/A – finite course of treatment.

8 Assessment of Safety

8.1 Specification of Safety Parameters

We anticipate that providing HCV care and treatment on site at a community syringe exchange center will allow access to treatment for greater numbers of people who inject drugs (PWID). Treatment on this study will include FDA-approved standard of care regimens with excellent safety profile; however limited data exists on the use of these agents in PWID. While experts have little concern for drug-drug interactions between most DAAs and illicit drugs, we have chosen to monitor HCV Treatment-related SAEs, Hospitalizations and Deaths related to Overdose, and Overall Deaths as safety endpoints that would trigger review of the study. Other on treatment side effects will also be captured and described, but will not impact conduct of the study and thus will not be reported to DSMB. Currently, HCV cure rates exceed 90% with currently available all oral DAA regimens in clinical trials and recent clinical cohorts regardless of HCV genotype; however little is known about treatment efficacy and safety in active drug users as these patients are typically excluded from clinical trials. One clinical trial of a modern era DAA regimen was conducted in 301 persons receiving opioid agonist therapy (OAT) (Merck C-EDGE Co-STAR) and provides some safety and efficacy data relevant to our study. It did not exclude patients who were actively using drugs of potential abuse, and more than 50% of patients had at least one urine drug screen positive for potential drugs of abuse. The study randomized patients to the fixed dose combination of elbasvir/grazoprevir or placebo, so that safety could be carefully ascertained in this patient population perceived as being high risk for unrelated adverse events. Those that received placebo were subsequently treated open label. The primary efficacy outcome showed an SVR 12 of 91.5% in the immediate treatment group and 89.5% in the delayed treatment group. Positive urine drug screens did not affect adherence or efficacy. 18 patients had recurrent viremia and 5 were due to probable reinfection. The safety profile was similar between treatment and placebo with rare SAEs (3.5% in treated, 4% in placebo); however, only 1 SAE in each group was considered treatment-related. The high efficacy and relative safety of this study of patients on OAT, many of who also used drugs of potential abuse, is reassuring that HCV treatment may be safely delivered to our study population.

8.1.1 Definition of Adverse Events (AE)

An **adverse event** (AE) is any symptom, sign, illness or experience that develops or worsens in severity during the course of the study. Intercurrent illnesses or injuries should be regarded as adverse events. Abnormal results of diagnostic procedures are considered to be adverse events if the abnormality:

- results in study withdrawal
- is associated with a serious adverse event
- is associated with clinical signs or symptoms
- leads to additional treatment or to further diagnostic tests
- is considered by the investigator to be of clinical significance

8.1.2 Definition of Serious Adverse Events (SAE)

Serious Adverse Event

Adverse events are classified as serious or non-serious. A **serious adverse event** is any AE that is:

- fatal

- life-threatening
- requires or prolongs hospital stay
- results in persistent or significant disability or incapacity
- a congenital anomaly or birth defect
- an important medical event

Important medical events are those that may not be immediately life threatening, but are clearly of major clinical significance. They may jeopardize the subject, and may require intervention to prevent one of the other serious outcomes noted above. For example, drug overdose or abuse, a seizure that did not result in in-patient hospitalization, or intensive treatment of bronchospasm in an emergency department would typically be considered serious.

All adverse events that do not meet any of the criteria for serious should be regarded as ***non-serious adverse events***.

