4.2.2 Secondary Study Endpoints

Aim 2: Substance use. We will report rates of addiction treatment entry and retention;

changes in levels of self-reported alcohol and illicit drug consumption; and urine toxicology results. Outcomes will be examined at 3, 6, and 9 months after randomization, to assess the magnitude and durability of intervention effects. Effect sizes and 95% CIs will be reported.

Aim 3: HIV and HCV risk behaviors. We will report changes in frequency of three injection related and three sexual HIV risk behaviors: (a) injection drug use, (b) use of a syringe previously used by another person, and (c) use of any injection equipment (cooker, cotton, mixing water, mixing syringe, rinse water) previously or simultaneously used by another person, (d) condomless vaginal or anal sex, (e) sex with multiple partners (≥ 2 in past 6 months), and (f) sex in exchange for money or drugs. Outcomes will be reported at 3, 6, and 9 months after randomization, to assess the possibility of transient intervention effects.

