8.3 Time Period and Frequency for Event Assessment and Follow-Up

The occurrence of an AE or SAE may come to the attention of study personnel during study visits and interviews of a study participant presenting for medical care, or upon review by a study monitor. All AEs including local and systemic reactions not meeting the criteria for SAEs will be captured on the appropriate RF. Information to be collected includes event description, time of onset, clinician's assessment of severity, relationship to study product (assessed only by those with the training and authority to make a diagnosis), and time of resolution/stabilization of the event. All AEs occurring while on study must be documented appropriately regardless of relationship. All AEs will be followed to adequate resolution.

Any medical condition that is present at the time that the participant is screened will be considered as baseline and not reported as an AE. However, if the study participant's condition deteriorates at any time during the study, it will be recorded as an AE. UPs will be recorded in the data collection system throughout the study.

Changes in the severity of an AE will be documented to allow an assessment of the duration of the event at each level of severity to be performed. AEs characterized as intermittent require documentation of onset and duration of each episode.

The PI will record all reportable events with start dates occurring any time after informed consent is obtained until 7 (for non-serious AEs) or 30 days (for SAEs) after the last day of study participation. At each study visit, the investigator will inquire about the occurrence of AE/SAEs since the last visit. Events will be followed for outcome information until resolution or stabilization.

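### Resumed or increased drug use can be logged as an SAE, while non-fatal, non-hospitalised overdoses lie outside the named review endpoints unless judged HCV treatment-related

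*Combined protocol and SAP*

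**What the plan says.** **What counts as serious.** Section 8.1.2 says that a serious adverse event "is any AE that is" fatal, life-threatening and so on, ending with important medical events. Its examples of that last group, described as typically serious, begin: "For example, drug overdose or abuse, a seizure that did not result in in-patient hospitalization". There is no exception for this study's population.

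**What counts as an adverse event.** Section 8.1.1 defines an AE as "any symptom, sign, illness or experience that develops or worsens in severity during the course of the study". Section 8.3 adds a baseline rule, "Any medical condition that is present at the time that the participant is screened will be considered as baseline and not reported as an AE", and qualifies it: "if the study participant's condition deteriorates at any time during the study, it will be recorded as an AE".

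**Who is enrolled and what is measured.** Section 5.1 requires people to have "injected heroin, cocaine, or other drugs in the past 30 days" (the Protocol Summary gives 90 days; the point is the same under either). Aim 2 in Section 4.2.2 reports "changes in levels of self-reported alcohol and illicit drug consumption" at 3, 6 and 9 months.

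**What prompts review.** Section 8.1 names HCV treatment-related SAEs and "Hospitalizations and Deaths related to Overdose, and Overall Deaths as safety endpoints that would trigger review of the study". Other on-treatment side effects are recorded but not sent to the DSMB.

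**What the DSMB sees.** Under Section 8.5 the board meets at least twice a year to look at safety and efficacy data by arm. The data elements are to be defined with a charter that the protocol describes as still to be written.

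**The concern.** Two things are left unsettled. First, a change in drug use is an outcome of this trial, yet the SAE definition names drug abuse as a typical serious event. A participant who reports injecting more often, or starting again after a break, could be recorded as an Aim 2 data point, a non-serious AE or an SAE, depending on who classifies the report. The trial is not blinded (Section 9.5) and only the Accessible Care arm receives its hepatitis care on site (Section 7.1), so classification could also drift between arms.

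Second, overdose is the one specific clinical event among the named review endpoints, so the investigators already regard it as important. But the endpoint is narrower than the seriousness definition. An overdose reversed in the community without admission meets the definition and not the endpoint. If such events are left out of the DSMB tables, the board sees only part of the overdose picture in each arm.

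**Working it through.** The plan gives no figure for either gap, so there is none to reproduce. The check is a reading of Sections 8.1, 8.1.1, 8.1.2, 8.3 and 8.5 together, followed by two illustrations.

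**Step 1. How each event is classified.**

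| Event during follow-up | AE (8.1.1, 8.3)? | SAE (8.1.2)? | Review endpoint (8.1)? |
|---|---|---|---|
| Drug use unchanged since entry | No, baseline | No | No |
| Drug use increased, or resumed after a break | Can be read as yes | Can be read as yes | Only if judged HCV treatment-related |
| Overdose, non-fatal, not hospitalised | Yes | Typically yes | Only if judged HCV treatment-related |
| Overdose, hospitalised | Yes | Yes | Yes |
| Overdose, fatal | Yes | Yes | Yes |

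The second and third rows carry the point. For a participant who never starts antivirals, the treatment-related route has no treatment to relate to. The illustration in Section 9.2 has 150 of 300 participants starting, so on that figure the route is closed for the other 150.

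**Step 2. How little it would take to change the SAE table (illustration).** Inputs: 300 randomised (Section 5.6), and the SAE rates that Section 8.1 quotes from a trial in people on opioid agonist therapy, 3.5% treated and 4% placebo. Background SAE participants are 300 × 0.035 = 10.5 or 300 × 0.04 = 12. Let f be the share of participants with drug use logged as an SAE, with no overlap with the background. The documents do not give f. At the 4% rate, the share of SAE participants due to drug use is 300f / (300f + 12):

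- f = 0: 0%
- f = 1%: 3 / 15 = 20%
- f = 4%: 12 / 24 = 50%
- f = 10%: 30 / 42 = 71%

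With the baseline rule applied to unchanged use, f could be close to zero. A higher background rate would lower these shares.

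**Step 3. How many non-fatal overdoses fall outside the overdose endpoint (illustration).** Let h be the share that are hospitalised, which the documents also do not give. If none is judged treatment-related, the share outside is 1 − h: 90% at h = 10%, 75% at 25%, 50% at 50%, 25% at 75% and 10% at 90%. It exceeds half only when h is below 50%.

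**The case against.** The strongest reply is that the sections do different jobs. Section 8.1.2 defines seriousness for recording; Section 8.1 picks a subset of events that prompt review and presents that as a deliberate choice. A trigger narrower than the SAE definition is normal and is not in itself a contradiction. That stands. What remains is that no section says whether the events outside the subset go to the board.

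Several stronger readings are tempting, and the documents do not support them:

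- *Ordinary drug use will swamp the SAE counts, with all 300 participants potentially affected.* An SAE must first be an AE, and unchanged use is baseline. Important medical events must also be of clear clinical significance, and the examples are only typically serious. Only resumed or increased use is open.
- *Most non-fatal overdoses are missed.* This needs the hospitalised share, which the documents do not give.
- *These overdoses never reach the DSMB.* Section 8.5 provides regular review of safety data by arm, and the Section 8.1 sentence on what is withheld concerns other on-treatment side effects, which does not clearly cover an overdose SAE. Missing the trigger is not shown to be missing review.
- *Such an overdose leads to no action at all.* Section 8.3 requires every AE to be documented and followed, and a reversed overdose could plausibly enter the IRB continuing-review table in Section 8.4.1 as a Grade 4 event.
- *Drug-use SAEs would flood the review trigger.* They would not, because the trigger counts SAEs only when HCV treatment-related.

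One further objection also stands. Admissions and deaths can be checked in records, whereas non-hospitalised overdoses rest largely on self-report in an unblinded trial. The Accessible Care arm has on-site medical visits and monitoring bloods, so ascertainment may be unequal.

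**Conclusion.** The point holds in a limited form. The SAE wording is not adapted to a population of active injectors, so resumed or increased drug use can be logged as an SAE and may inflate the counts. Separately, a non-fatal, non-hospitalised overdose not judged HCV treatment-related is an SAE outside the named review endpoints, and its route to the DSMB depends on a charter that the protocol leaves to be written and that is not among the documents.

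The size of either effect cannot be stated from the documents. The 50% figure at f = 4% rests on an assumed f, no overlap, and a background rate borrowed from another trial; it shows sensitivity and is not a forecast. The SVR endpoint and its analysis are untouched. This is an inexpensive improvement to safety monitoring and does not undermine the trial's main comparison.

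**What to change.** In Section 8.1.2, delete 'or abuse', keep overdose, and state that continuing, resumed or increased drug use is an Aim 2 outcome and not in itself an SAE.

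In Sections 8.1 and 8.5, state that all overdoses are reported to the DSMB by arm in three rows: fatal, hospitalised, and non-hospitalised. Leave the existing hospitalisation and death trigger as it is. Carry the same list into the DSMB charter.

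The cost is wording in a few sections and one more row in the DSMB tables. Section 8.3 already has adverse events asked about at every study visit, so no new contact is needed. The downside is the uneven ascertainment noted above. A footnote should tell the board to read the non-hospitalised row with that in mind; keeping it separate prevents it from blurring the better-verified counts.
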